Both opponents and advocates of PSA-based screening acknowledge that screening increases the detection of prostate cancer. An important assumption underlying the USPSTF recommendation against screening is that men with indolent cancer will continue to receive unnecessary treatment. An important assumption underlying the AUA recommendation for screening is that patients and physicians will be able to uncouple the diagnosis of prostate cancer from treatment. For example, men at highest risk for death from prostate cancer will receive treatment. All other men will undergo a period of active surveillance (AS). During followup on AS, men with evidence of high risk disease or cancer progression are offered definitive local therapy; however, men who continue to have low risk cancer can delay or completely avoid treatment. A barrier to AS is that clinical tools for risk-stratifying and monitoring men with newly diagnosed prostate cancer have limited accuracy. Prostate cancers are multifocal and biopsies are vulnerable to sampling error. Transrectal ultrasound-guided (TRUS) biopsy remains the gold standard for diagnosing prostate cancer and monitoring patients on AS. However, the standard prostate biopsy may miss clinically significant disease. TRUS biopsy understages the cancer in approximately a third of patients.^{20, 21} Furthermore, TRUS biopsy is accompanied by complications such as systemic infection, bleeding, and transient erectile dysfunction.²² **There is a clear need for innovations to reduce the clinical burden of diagnosing and monitoring prostate cancer.**

3.0 STUDY DESIGN:

A. Overview

Prostate cancer is the rare malignancy where there is no imaging strategy to serially monitor the tumor. MRI, which is the best tool we have for imaging the prostate, cannot detect most tumors and does not have the resolution to detect subtle changes in tumor size or tumor characteristic. Therefore, followup during AS relies on serial transrectal biopsies. An effective imaging strategy will decrease the clinical burden of AS. This prospective trial will compare the effectiveness of high resolution MRI (hrMRI) and standard MRI (sMRI) for serially monitoring prostate tumors for clinical progression, which is an indication for definitive local therapies such as radical prostatectomy and external beam radiotherapy. **We test the hypothesis that hrMRI may detect changes in tumor size or ADC value, which will predict clinical progression as defined by biopsy criteria.**

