B. Study Population

The study population for recruitment will be patients at Cedars-Sinai Medical Center with prostate cancer on active surveillance.

C. Inclusion/Exclusion Criteria

Inclusion Criteria:

[figure not shown]
- Age over 18 years
- Patients diagnosed with clinically localized prostate cancer
- Low or Low-intermediate Risk Prostate cancer¹ defined as:
 - Pre-operative PSA \leq 20.0 ng/ml
 - Clinical stage cT1 or cT2
 - Gleason score 3+3 or 3+4
- Patients choosing AS or already on AS as primary management strategy
- No previous treatment for prostate cancer with radiotherapy, chemotherapy, or hormonal therapy
- No contraindications for gadolinium enhanced MRI

D. Study endpoints

Primary Endpoint: evidence of disease progression as defined by any of the following:

- Increase in Gleason score from 3 + 3 to Gleason sum 7 on biopsy
- Gleason score 4+3 on biopsy
- Gleason sum 8-10 on biopsy
- ≥ 3 Increase in number of positive cores
- Progression to nodal or bone involvement

E. Study Design

The study enrolls patients with low and low-intermediate risk prostate cancer. The National Comprehensive Cancer Network (NCCN) guidelines for prostate cancer list AS as an option for these patients.¹ There is no proven standard for monitoring patients on AS. The NCCN recommends a standard 12-core prostate biopsy every 1-2 years, at the discretion of the treating physicians depending on risk category and length of stable followup on AS. All Patients enrolling on the study will undergo standard (control) MRI (sMRI) and experimental High-Resolution MRI (hrMRI) at the time of study enrollment and again in 12 months (+/- 2 months). The patients then undergo a standard ultrasound guided 12-core prostate biopsy, where prostate ultrasound is used to sample 2 cores from the left and right lobes at the base, midgland and apex. At the discretion of the treating physician, the 2nd MRI and biopsy may be performed early if disease progression is suspected due to increasing PSA or adverse change in prostate exam. These for-cause MRI and biopsies will be used for the final analysis if the interval between MRIs is at least 5 months.

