All MRI images will be read according to PI-RADS (version 2). All lesions with PI-RADS greater than or equal to 3 will be considered suspicious for cancer. A region of interest (ROI) application will be used. The circumference of a suspicious lesion will be drawn on each individual MRI slice. The lesion volume and average ADC will be calculated from the ROI's. At the discretion of the treating physician, the MRI images may be used to perform a MRI-ultrasound fusion biopsy of suspicious lesions, however, only the standard 12-core biopsy will be used for the statistical analysis.

Study calendar

| Study Calendar | |
|--------------------------------|--|
| Registration/consenting | |
| Standard and experimental MRI | |
| Standard and experimental MRI* | 12 months after first MRI (+/- 2 months) |
| Prostate biopsy* | within 3 months of the 2 nd MRI |

* At the discretion of the treating physician, the 2nd MRI and biopsy may be performed early if disease progression is suspected due to increasing PSA or adverse change in prostate exam.

F. Study Risks

All agents administered to patients in this study are approved by the U.S. Food and Drug Administration. This study investigates a novel software-based MRI imaging protocol that improves image resolution.

Magnetic Resonance Imaging (MRI)

MRI imaging is among the least invasive of all imaging modalities. The U.S. Food and Drug Administration has labeled MR systems of up to 4.0 Tesla as having “non-significant risk” and currently there is no evidence that MR imaging causes any long-term or irreversible effects in human beings. However, there are certain risks, which are detailed below.

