Preliminary data from 13 patients with a total of 14 Gleason score 6 lesions show a mean of 0.19 cm³ and standard deviation of 0.19 cm³. We expect to detect at least a 50% increase in tumor volume in the group who progress compared to the group of patients that do not progress relative to baseline. Assuming that the standard deviation at the biopsy/MRI is similar to the baseline biopsy/MRI, group sample sizes of 12 patients who progressed and 47 patients that do not progress achieve 91% power to detect a difference in the mean change tumor volume around 0.285 cm³ at the two-sided two-sample t-test with a 0.05 level of significance. The estimate standard deviation of the difference in tumor size in each group (SDdiff) was estimated assuming the correlation coefficient measurements is 0. Since this correlation coefficient is likely to be positive, this power calculation is very conservative and much smaller mean change tumor volume can be detected. In fact, if this correlation coefficient equals to 0.6, then we can achieve 90% power to detect a mean change tumor volume around 0.18 cm³. With respect to change in ADC, preliminary data show that the mean and SD of ADC are 0.2 and 0.05, respectively. Under similar assumptions for the correlation coefficient between the first and second measurements (corr = 0), group sample sizes of 12 patients who progressed and 47 patients that do not progress achieve 80% power to detect a difference in the mean change ADC around 0.07 at the two-sided two-sample t-test with a 0.05 level of significance. This corresponds to about a 50% increase in ADC between the two groups of patients.

Multivariable logistic regression model will be used to study the association between change in tumor size and ADC from the first and the second biopsy as assessed by imaging and disease progression adjusting for potential baseline characteristics such as PSA level, clinical stage, NCCN risk category, and size of prostate nodule. Tumor size

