and ADC is measured by averaging the volumes or ADCs of all detectable lesions (PI-RADS 3 - 5). Secondary analyses include studying this association by considering changes of single lesions. Automatic variable selection methods such as backward and stepwise selection will be used as a guideline to identify sets of important predictors of progression. More rigorous approach based on a 4-step procedure outlined in Collett²⁴ will be employed. Several model checking diagnostics will be employed to ensure that the logistic model is appropriate.²⁵

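### Does pooling for-cause second MRIs from 5 months with the 10–14 month scans call for an added check in the analysis plan?

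*Combined protocol and SAP*

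**What the plan says.** Section 3.0 E puts the second standard and high-resolution MRI at 12 months, plus or minus 2, so scheduled pairs are 10 to 14 months apart. At the treating physician's discretion, "the 2nd MRI and biopsy may be performed early if disease progression is suspected due to increasing PSA or adverse change in prostate exam". Such pairs are kept subject to a floor: "These for-cause MRI and biopsies will be used for the final analysis if the interval between MRIs is at least 5 months". The footnote to the study calendar repeats the early option.

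Section 3.0 G plans a multivariable logistic regression to "study the association between change in tumor size and ADC from the first and the second biopsy as assessed by imaging", "adjusting for potential baseline characteristics such as PSA level, clinical stage, NCCN risk category, and size of prostate nodule". The covariate list is open but confined to baseline items, so it covers neither the interval between MRIs nor for-cause status. The one secondary analysis named concerns single lesions. The hypothesis in section 3.0 A is that "hrMRI may detect changes in tumor size or ADC value, which will predict clinical progression as defined by biopsy criteria".

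**The concern.** The analysis set may hold intervals from 5 to 14 months, a 2.8-fold range (14/5), and the short ones arise because progression was suspected. PSA and prostate examination are not endpoint criteria, so early scanning does not fix the outcome, but observed time is probably shorter in men who progress. If lesions grow with time, unscaled change is then understated in the group expected to show more of it. With about 12 progressors planned, a few early scans could move the estimate, and a reader of the results could not tell whether they had. Section 2.0 also speaks of tumor growth kinetics as a possible prognostic tool, which makes elapsed time look like something the model should carry.

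**Working it through.** **Inputs from section 3.0 G.** 12 progressors and 47 non-progressors; volume SD 0.19 cm³; target difference in mean change 0.285 cm³; correlation r between the two measurements 0; two-sided 5% t-test; stated power 91%. There is a second target: "if this correlation coefficient equals to 0.6, then we can achieve 90% power to detect a mean change tumor volume around 0.18" cm³.

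**The plan's own figures.** SD of change = 0.19 × √(2(1−r)), which is 0.269 at r = 0 and 0.170 at r = 0.6. Standard error = SD × √(1/12 + 1/47), which is 0.0869 and 0.0550. Power for 0.285 at r = 0 is 90.7% by the normal approximation and 89.7% by exact noncentral t, so the stated 91% reproduces. Power for 0.18 at r = 0.6 is 90.6% and 89.6%, against 90% stated.

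**Dilution.** Assumptions not in the documents: linear growth, no mean growth in non-progressors, a share p of progressors scanned early at a mean of 7 months, the rest at 12, and early-scanned men growing m times as fast as other progressors. Difference = 0.285 × [(1−p) + p × m × 7/12].

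| p (m = 1) | Difference, cm³ | Power, r = 0 | r = 0.3 | r = 0.6 |
|---|---|---|---|---|
| 0 | 0.285 | 89.7% | 97.1% | 99.9% |
| 1/3 | 0.245 | 79.3% | 91.3% | 99.2% |
| 1/2 | 0.226 | 72.3% | 86.2% | 98.1% |

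For the 0.18 target at r = 0.6 the difference becomes 0.155 and 0.143, with power 79% and 72%.

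**Direction.** The loss vanishes when m × 7/12 = 1, that is m = 1.71. At m = 2 the difference is 0.301 (p = 1/3) or 0.309 (p = 1/2), above the target. The early scan is triggered by suspected progression, so faster growth in these men is plausible.

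**False positives.** Suppose instead that everyone grows 0.19 cm³ a year and 6 of 12 progressors are scanned at 5 months. The difference in mean change is −0.19 × (6/12) × (1 − 5/12) = −0.055 cm³. In standard errors this is −0.055/0.0869 = −0.64 at r = 0 and −0.055/0.0550 = −1.01 at r = 0.6. A nominal 5% test then rejects about 9.5% and 16% of the time. Nearly all of these rejections point to less growth in progressors. The upper tail, by the normal approximation, is P(Z > 1.96 + 0.64) = 0.5% and P(Z > 1.96 + 1.01) = 0.15%.

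**What a restricted analysis could show.** Keep only pairs 10–14 months apart, and assume 5% of non-progressors were early, leaving about 45. Progressors fall to 8 (p = 1/3) or 6 (p = 1/2). The restricted set is nested in the full set, so the variance of the gap between the two estimates is SD² × [(1/n − 1/12) + (1/45 − 1/47)].

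| n | 95% margin of gap, r = 0 | r = 0.6 | Expected gap |
|---|---|---|---|
| 8 | ±0.11 cm³ | ±0.07 cm³ | 0.285 − 0.245 = 0.04 cm³ |
| 6 | ±0.15 cm³ | ±0.10 cm³ | 0.285 − 0.226 = 0.06 cm³ |

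The margin exceeds the expected gap in every row. Power for 0.285 in the restricted set at r = 0 is about 76% or 64%.

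**The case for a change.** The strongest case for acting is that the interval must already be recorded to apply the 5-month rule, so a table and one extra model run cost almost nothing, and fixing them in advance stops anyone choosing a subset after seeing results. The omission is real, and false positives cannot be waved away: under equal growth they can reach the 9.5% to 16% shown above. That much stands.

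The restricted run, however, would not answer the question. It selects by interval, so a for-cause scan at 10 or 11 months stays in, while the men removed were selected on rising PSA or examination change. Interval and case mix shift together, and a gap could not be put down to either. Excluding for-cause pairs as well would separate the two no better and would leave fewer progressors.

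Dividing change by time is no clear gain. Short intervals magnify measurement noise; in simulation a pooled t-test on annualised values rejected 8–10% of the time when noise dominated, though Welch's test held about 5%. Also, "ADC is measured by averaging the volumes or ADCs of all detectable lesions", so a new small lesion can lower the average and a rate built on it would not be a growth rate. The interval table is worth having, but it is descriptive and alters no estimate.

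**Conclusion.** No change to the plan follows. Keeping for-cause pairs is a fair trade-off: the rule is stated in advance with a floor, and it retains men likely to supply part of the roughly 12 events. Change, not growth rate, is what the hypothesis names, so the planned analysis remains a test of that hypothesis.

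The possible loss is 0.04–0.06 cm³ on 0.285 if one third to one half of progressors are scanned at about 7 months and grow linearly at the same rate as the rest. It is nil or reversed if they grow more than 1.71 times as fast. The documents supply none of these quantities. The sums use the protocol's t-test setting rather than its logistic model, and volume only; the documents give no basis for a matching ADC figure. The available check has a margin wider than the loss, so it would detect only a large dependence on early scans. Analysts can report months between MRIs by progression and for-cause status without an amendment, and readers should weigh the result with that table in view.

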| Diagnosis and Main Inclusion Criteria | 
Inclusion Criteria:
 
 • Age over 18 years • Patients diagnosed with clinically localized prostate cancer • Low or Low-intermediate Risk Prostate cancer¹ defined as: 
 ◦ Pre-operative PSA \leq 20.0 ng/ml ◦ Clinical stage cT1 or cT2 ◦ Gleason score 3+3 or 3+4 • Patients choosing AS or already on AS as primary management strategy • No previous treatment for prostate cancer with radiotherapy, chemotherapy, or hormonal therapy • No contraindications for gadolinium enhanced MRI |
| Study Imaging | Standard multiparametric prostate MRI with high resolution diffusion weighted imaging |
| Control Imaging | Standard multiparametric prostate MRI |
| Reference standard | Evidence of disease progression on standard 12-core ultrasound-guided prostate biopsy. |
| Statistical analysis | 
Our hypothesis is that changes in tumor size or apparent diffusion coefficient (ADC) on high resolution MRI will predict presence of biopsy criteria for disease progression.
 
59 patients achieve 91% power to detect a 0.285 cm^3 difference (between patients progressing and patients not progressing) in the mean change in tumor volume at the two-sided two-sample t-test with a 0.05 level of significance. With respect to change in ADC, 59 patients achieve 80% power to detect a difference in the mean change ADC around 0.07 at the two-sided two-sample t-test with a 0.05 level of significance. This corresponds to about a 50% increase in ADC between the two groups of patients.
 |

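### Section G expects at least a 50% volume increase (0.095 cm³) but quotes 91% power for 0.285 cm³, which is 150% of baseline; power at 50% is about 19% at correlation 0 and 40% at 0.6

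*Combined protocol and SAP*

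**What the plan says.** All the relevant statements are in the power paragraphs of Section 3.0 G, Statistical Analysis, except where noted.

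- **Baseline.** Pilot data from 13 patients: "14 Gleason score 6 lesions show a mean of 0.19" cm³, with an SD also of 0.19 cm³.
- **Expected effect.** As a minimum, "a 50% increase in tumor volume in the group who progress compared to the group of patients that do not progress relative to baseline".
- **Powered effect.** With 12 progressors and 47 non-progressors, the plan says these groups "achieve 91% power to detect a difference in the mean change tumor volume around 0.285 cm³"; the comparison is evaluated "at the two-sided two-sample t-test with a 0.05 level of significance". The SD of the change assumes zero correlation between the two scans.
- **Reassurance.** Because the correlation is probably positive, "this power calculation is very conservative and much smaller mean change tumor volume can be detected". At a correlation of 0.6, "we can achieve 90% power to detect a mean change tumor volume around 0.18" cm³.
- **Study Summary, Statistical analysis row.** "59 patients achieve 91% power to detect a 0.285 cm^3 difference" in mean change between progressing and non-progressing patients. The Summary does not mention a 50% volume increase.

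**The concern.** The same paragraph describes the target volume effect in two ways that do not agree. Relative to the only baseline volume in the document, 0.19 cm³, a 50% increase is 0.095 cm³. The power calculation uses three times that. The alternative effect of 0.18 cm³ is about 95% of baseline, so it does not correspond to 50% either.

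Change in tumor size is one of the two imaging changes in the study hypothesis, and the justification for 59 patients leads with this power statement. Someone reading the sentences in order would conclude that a 50% growth difference is detectable with about 91% power, or more given the remark about conservatism. If the volume comparison then came out null, it could be taken as evidence against a 50% difference when the design had little chance of showing one.

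**Working it through.** **Inputs, all from Section 3.0 G.** Mean 0.19 cm³; SD 0.19 cm³ at each scan; correlation r = 0 or 0.6; groups of 12 and 47 (20% of 59 is 11.8, rounded to 12); two-sided α = 0.05. The correlations 0.3 and 0.8 below are my sensitivity values and are not in the plan.

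**Effect sizes against baseline**

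- 50% of baseline: 0.5 × 0.19 = 0.095 cm³
- Powered effect: 0.285 / 0.19 = 1.50, so 150% of baseline
- Alternative effect: 0.18 / 0.19 = 0.95, so 95% of baseline
- Base volume for which 0.285 would be 50%: 0.285 / 0.5 = 0.57 cm³, a volume the document does not give

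**Method.** The SD of the change is SDdiff = 0.19 × √(2(1 − r)). The standard error of the group difference is SDdiff × √(1/12 + 1/47) = SDdiff × 0.3234. Power comes from the noncentral t distribution with 57 degrees of freedom (critical value 2.0025) and noncentrality equal to the difference divided by the standard error.

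**Reproducing the plan's figures**

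- r = 0: SDdiff = 0.2687, SE = 0.0869, noncentrality 0.285 / 0.0869 = 3.28. Power is 89.7% (about 90.7% by normal approximation), against 91% stated.
- r = 0.6: SDdiff = 0.1699, SE = 0.0550, noncentrality 0.18 / 0.0550 = 3.27. Power is 89.6% (about 90.6% by normal approximation), against 90% stated.

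Both stated figures are reproduced to within about 1.5 percentage points, so the plan's method is clear and its arithmetic is sound for the differences it entered.

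**The same method at 0.095 cm³**

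| Correlation | SDdiff (cm³) | Noncentrality | Power |
|---|---|---|---|
| 0 (plan) | 0.2687 | 1.09 | 18.9% |
| 0.3 (assumed) | 0.2248 | 1.31 | 25.0% |
| 0.6 (plan) | 0.1699 | 1.73 | 39.7% |
| 0.8 (assumed) | 0.1202 | 2.44 | 67.1% |

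Solving for the correlation, power at 0.095 cm³ reaches 50% at r ≈ 0.70, 80% at r ≈ 0.85 and 90% at r ≈ 0.89.

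**Smallest difference detectable with 80% power, 12 versus 47.** 0.248 cm³ (130% of baseline) at r = 0; 0.157 cm³ (82%) at r = 0.6; 0.111 cm³ (58%) at r = 0.8.

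**If all 80 subjects in the Study Summary count.** Assuming all are evaluable and 20% progress (16 versus 64), power at 0.095 cm³ is 23.9% at r = 0, 50.6% at r = 0.6 and 79.8% at r = 0.8.

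**The case against.** The best defence is that the power statement is correct for the effect it names, and that effect is given openly in cm³ in both places. The expectation is worded as a minimum, so a 0.285 cm³ difference does not strictly contradict it. The Summary makes no 50% claim for volume and is not wrong as it stands. The 0.19 cm³ mean comes from Gleason 6 lesions only, whereas the trial also admits Gleason 3+4, so the enrolled baseline may differ. If the 50% phrase is itself the slip, the low-power argument falls away and one loose sentence remains. The remark about conservatism is already tied to the correlation in its own sentence.

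Much of this is fair. It is not possible to tell from the document which figure was intended. That 0.285 equals 1.5 × 0.19 suggests that a final volume was entered as a change, but this is inference. The zero-correlation choice is indeed conservative. The SD is also imprecise: treating the 14 lesions as independent and normal, its 95% interval is about 0.14 to 0.31 cm³, which puts power at 0.095 cm³ between about 10% and 32% at r = 0 and between 18% and 65% at r = 0.6. The tenths of a percent in the table should not be taken literally.

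None of it removes the mismatch. A minimum of 50% makes 50% the smallest effect the plan says it expects to detect, and power there stays below 80% at both of the plan's correlations across that whole SD interval. The document gives no other baseline volume and no reason to expect a 150% difference.

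**Conclusion.** The concern holds. The quoted 91% belongs to a difference of 150% of baseline, not to the 50% expectation stated just before it. At 50%, the t-test used for sizing has about 19% power at correlation 0 and about 40% at 0.6; counting all 80 subjects raises these only to about 24% and 51%. Adequate power would need a between-scan correlation of about 0.85 or more, which the plan neither estimates nor assumes.

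This rests on 0.19 cm³ being the baseline meant, on an SD of 0.19 cm³ at both scans, and on the 12/47 split. It concerns the sizing t-test only. The planned analysis is a multivariable logistic regression, for which the plan gives no power. The statement needs correcting because the sample-size justification rests on it, although the correction is one of wording.

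**What to change.** In Section 3.0 G, do one of the following.

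- **(a) Keep the powered effect.** State that the design is powered for 0.285 cm³, a 150% increase over the 0.19 cm³ pilot mean at correlation 0 (and for 0.18 cm³, about 95%, at correlation 0.6). Remove the 50% expectation as the powered effect. The Study Summary can stay as it is.
- **(b) Keep 50%.** Write it as 0.095 cm³ and give the power as about 19% at correlation 0 and 40% at 0.6. Add about 25% at 0.3 and 67% at 0.8, labelled as sensitivity values, and note that 90% needs about 0.89. Say that these depend on an SD from 14 lesions. Change the 0.285 cm³ / 91% statement in the Study Summary to match.

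Under either option, describe the calculation as conservative with respect to the correlation only, so that it does not suggest adequate power for a 50% increase.

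The cost is a few sentences in Section G, plus the Summary under (b), and a less favourable stated effect (a) or stated power (b). Enrolment, scans, endpoint and analysis are unchanged.

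### Does the plan misstate the detectable ADC difference when it calls about 0.07 a 50% increase?

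*Combined protocol and SAP*

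**What the plan says.** Section 3.0 G, Statistical Analysis, gives the ADC inputs: "preliminary data show that the mean and SD of ADC are 0.2 and 0.05, respectively". It takes the correlation between the two measurements as zero, as it does for tumor volume, and says that "group sample sizes of 12 patients who progressed and 47 patients that do not progress achieve 80% power". The effect is "a difference in the mean change ADC around 0.07 at the two-sided two-sample t-test with a 0.05 level of significance". The next sentence turns that absolute difference into a relative one: "This corresponds to about a 50% increase in ADC between the two groups of patients".

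The Statistical analysis row of the Study Summary repeats the claim ("59 patients achieve 80% power to detect a difference in the mean change ADC around 0.07") and the 50% sentence, but prints no ADC mean.

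The volume part of section 3.0 G does attach a reference to its percentage. It speaks of "a 50% increase in tumor volume in the group who progress compared to the group of patients that do not progress relative to baseline".

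Neither place gives an expected ADC for either group, or says whether ADC should rise or fall in patients who progress.

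**The concern.** A reader who wants to check the 50% will divide 0.07 by the one ADC mean available, 0.2, and get 35%. Half of 0.2 would be 0.10, for which the same design has about 99% power rather than 80%. On that reading the plan calls the detectable effect a half when its own inputs give a third.

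This is the plan's only relative description of the ADC effect, and ADC change is one of the two imaging measures in the hypothesis. Someone judging whether the detectable effect is plausible might lean on it, above all in the Study Summary, where there is no mean to check it against. The volume sentence, which mentions baseline, makes the missing base for ADC more noticeable.

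**Working it through.** **Inputs (section 3.0 G).** ADC mean 0.2 and SD 0.05; correlation 0; groups of 12 and 47; two-sided two-sample t-test at 0.05.

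**Step 1: reproduce the plan's power figure.**
- SD of the change: 0.05 × √(2 × (1 − 0)) = 0.0707.
- Standard error of the difference in mean change: 0.0707 × √(1/12 + 1/47) = 0.0707 × 0.3234 = 0.0229.
- Normal approximation to the 80%-power difference: (1.960 + 0.842) × 0.0229 = 0.0641.
- Noncentral t with 57 degrees of freedom: 0.0652.
- Power by noncentral t: 79.8% at 0.065, 85.3% at exactly 0.07, 99.0% at 0.10.

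The 80%-power difference rounds to 0.07, so the plan's pairing of 80% with around 0.07 reproduces.

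**Step 2: the percentage under each base.**

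| Reading of the 50% | Calculation | Result |
|---|---|---|
| Difference over the preliminary mean, unrounded | 0.0652 / 0.2 | 33% |
| Difference over the preliminary mean, as printed | 0.07 / 0.2 | 35% |
| Higher group over lower group, higher at 0.2, unrounded | 0.0652 / (0.2 − 0.0652) = 0.0652 / 0.1348 | 48% |
| Higher group over lower group, higher at 0.2, as printed | 0.07 / (0.2 − 0.07) = 0.07 / 0.13 | 54% |

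The last two rows suppose that both groups start at 0.2, that one does not change, and that the other falls by the detectable difference. The difference in mean change is then also the difference between the follow-up means, and the percentage is the higher mean relative to the lower. If instead one group rose from 0.2 to 0.27, the percentage would be 0.07/0.2 = 35% again. The result therefore turns on the direction of change, which the plan does not state.

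**Step 3: rounding.** The mean is printed to one decimal, so it could lie between 0.15 and 0.25. With a difference between 0.065 and 0.075, the ratio to the mean runs from 0.065/0.25 = 26% to 0.075/0.15 = 50%. At a mean of 0.15, the printed 0.07 is already 47%. Rounding alone could account for the statement, but only with a mean near the bottom of its range.

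**Step 4: is the volume sentence a benchmark?** The volume difference printed with the 50% is 0.285 cm³, against a baseline mean of 0.19 cm³. 0.285/0.19 = 150%, and 50% of 0.19 would be 0.095. So the volume passage does not show that the plan's percentages are fractions of the preliminary mean, and it cannot settle the base for ADC.

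**Step 5: what uses the percentage.** The power calculation uses the absolute difference, the SD, the correlation, the group sizes and the significance level. The logistic regression uses each patient's observed changes. Neither uses the 50%.

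**The case for a change.** The case for a correction is that 0.07 is a difference in mean change, so baseline is the natural reference, and 0.2 is the only baseline value printed. The lower-group base of about 0.13 appears nowhere, and reaching it requires a direction of change that the plan never gives. Even a generous reading of about does not stretch from a third to a half. A one-sided test or a positive correlation makes the detectable difference smaller and moves the ratio to 0.2 further from 50%. The remedy would cost one sentence in two places.

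Most of this stands as far as it goes. The base is missing, and on the preliminary mean the figure is about a third. What does not follow is that the 50% is wrong. Dividing by 0.2 is also an inference, since nothing in the plan says the percentage is relative to that mean. The sentence speaks of an increase between the two groups, which fits a group-to-group ratio at least as well. That ratio comes to about 50% from the printed inputs once a direction is supposed. The group-to-group reading is available rather than proven, and so is the other.

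**Conclusion.** No change to the plan is needed. The 50% is ambiguous, not shown to be an error: it is 33–35% relative to the preliminary mean of 0.2, and 48–54% as a ratio of the higher to the lower group with the higher at 0.2. The second range assumes a common starting mean of 0.2 and a fall in one group only. The documents neither state nor rule out that assumption.

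The gap has no consequence for the trial. The absolute effect reproduces (0.0652, printed as around 0.07), and section 3.0 G prints everything needed to recompute the power. Under either reading the 59 patients, the 80% power, the test, the significance level and the regression are the same, and so are the results the trial will report. Naming the base, or leaving the percentage out, would be an editorial courtesy if the document were being revised for another reason.
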